7.4.1.2 Supportive analysis

As a supportive analysis, the linear mixed model described in the previous section (7.4.1.1) will also be fitted to observed and imputed data for the mITT population. Thus, a multiple imputation procedure will be set up and is described below.

First, in case of non-monotone missing data pattern, a MI procedure will be applied using a MCMC algorithm to create 20 imputed datasets with a monotone missing data pattern. The number of burnin iterations before each imputation will be set to 200. Sample SAS code is displayed below.

Sample SAS Code

```
proc mi data=DATWIDE nimpute=20 seed=111 out=MONODAT;

var TRTGRP GENETIC_MUT BASELINE CHANGE8 CHANGE24 CHANGE48;

mcmc chain=MULTIPLE impute=MONOTONE nbiter=200;

run;
```

Second, the 20 datasets with a monotone missing data pattern will be fully imputed based on a monotone method. Corresponding sample SAS code is provided below.

Sample SAS Code

```
proc mi data= MONODAT nimpute=1 seed=222 out=MONODAT;

by _IMPUTATION_;

class TRTGRP GENETIC_MUT;

var TRTGRP GENETIC_MUT BASELINE CHANGE8 CHANGE24 CHANGE48;

monotone regression (CHANGE8 CHANGE24 CHANGE48);

run;
```

Finally, the linear mixed model described in section 7.4.1.1 will be applied for each complete data sets producing 20 analysis results. The final treatment effect estimate will be obtained combining these 20 estimates as follows:

CER-001-CLIN-009 CER-001

Sample SAS Code

```
proc mianalyze data=MRESULTS_;

modeleffects ESTIMATE;

stderr STDERR;

ods output parameterestimates=RESULTS_;

run;
```

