7.4.1.3 Sensitivity analyses

7.4.1.3.1 Missing Not At Random data mechanism

These sensitivity analyses require partitioning the analysis mITT population into groups, based on treatment group and available information about the reasons for missing values, before multiple imputation.

Control-based I: all dropouts grouped with placebo

In the first control-based sensitivity analysis, all monotone missing values will be imputed such as all dropouts and the placebo group form a subset with similar trajectories. A dataset, MONOREF_all, containing all the placebo group subjects and the treatment group subjects with missing data, will be imputed as shown in sample SAS code below. The complement of MONOREF_all will be the complete observation treated group data, so this could be concatenated with the 20 imputed datasets in DATIMP1.

Sample SAS Code

```
proc mi data= MONOREF_all nimpute=1 seed=333 out=DATIMP1;
by _IMPUTATION_;
class GENETIC_MUT;
var GENETIC_MUT BASE CHANGE8 CHANGE24 CHANGE48;
monotone regression (CHANGE8 CHANGE24 CHANGE48);
run;
```

Control-based II (informative-dropout): poor-outcome dropouts grouped with placebo

In the informative-dropout sensitivity analysis, some subjects are characterized as likely to have poor unobserved outcomes, for example if study withdrawal is due to clinical worsening. In this case, the datasets in MONODAT (monotone dataset) will be first split by treatment groups, either randomized to the experimental (TRTGRP) or reference/placebo (REF) condition, and then the poor-outcome dropouts will be shifted to the REF group, resulting in the datasets MONOTRT_minus and MONOREF_plus. The multiple imputation will be conducted separately for each subset as shown in the following sample code. The output datasets, DATIMP2T and DATIMP2R, will simply be concatenated before the analysis step.

```
proc MI data= MONOTRT_minus nimpute=1 seed=444 out=DATIMP2T;
by _IMPUTATION_;
class GENETIC_MUT;
var GENETIC_MUT BASE CHANGE8 CHANGE24 CHANGE48;
monotone regression (CHANGE8 CHANGE24 CHANGE48);
run;

proc MI data= MONOREF_plus nimpute=1 seed=555 out=DATIMP2R;
by _IMPUTATION_;
class GENETIC_MUT;
var GENETIC_MUT BASE CHANGE8 CHANGE24 CHANGE48;
monotone regression (CHANGE8 CHANGE24 CHANGE48);
run;
```

Control-based III: poor-outcome dropouts act like reference

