In the third control-based sensitivity analysis, the MNAR statement will be used to allow poor-outcome subjects to follow the expected trajectory of a subject in the reference group (see sample code below). Since the treated subjects from MONOTRT_minus are treated similarly as in the informative-dropout scenario, the results here in DATIMP3R could be contatenated with DATAIMP2T for analysis.

```
proc MI data= MONOREF_plus nimpute=1 seed=666 out=DATIMP3R;
by _IMPUTATION_;
class GENETIC_MUT;
var GENETIC_MUT BASE CHANGE8 CHANGE24 CHANGE48;
monotone regression;
mnar model (CHANGE8 CHANGE24 CHANGE48) / modelobs=(TRTGRP="REF");
run;
```

For each scenario, every 20 analysis estimates will be combined in one final estimate.

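### The SAP's sample code overwrites the monotone dataset with fully imputed data, so the control-based sensitivity analyses, run in the printed order, would have nothing left to impute

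*SAP*

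**What the plan says.** SAP 7.4.1.2 imputes in two steps. Step 1 makes the missing pattern monotone and stores 20 datasets: "proc mi data=DATWIDE nimpute=20 seed=111 out=MONODAT". Step 2 completes them; the text reads "Second, the 20 datasets with a monotone missing data pattern will be fully imputed based on a monotone method", and the code is "proc mi data= MONODAT nimpute=1 seed=222 out=MONODAT". The step-2 model lists the patient's own arm among its variables ("var TRTGRP GENETIC_MUT BASELINE CHANGE8 CHANGE24 CHANGE48"), so a treated dropout is imputed as a treated patient. That is the MAR analysis.

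SAP 7.4.1.3.1 then describes three control-based analyses. The population is to be partitioned "based on treatment group and available information about the reasons for missing values, before multiple imputation".

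- **Control-based I** uses MONOREF_all, "containing all the placebo group subjects and the treatment group subjects with missing data". Its parent dataset is not named.
- **Control-based II** names its parent: "the datasets in MONODAT (monotone dataset) will be first split by treatment groups". The split gives MONOTRT_minus and MONOREF_plus.
- **Control-based III** reuses MONOREF_plus with the statement "mnar model (CHANGE8 CHANGE24 CHANGE48"), and its output is joined to the treated-arm output of II.

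**The concern.** The same name is given to two different objects: data with gaps, and data without. The control-based analyses need the first, but after step 2 only the second exists. No printed line keeps or rebuilds the monotone version.

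An imputation call on complete data returns the data unchanged. The control-based results would then match the MAR supportive result in both estimate and standard error, and could be reported as showing robustness to dropout when no alternative assumption had been applied. The main model (7.4.1.1) and the supportive analysis (7.4.1.2) both rest on MAR, and 7.4.1.3.2 repeats both in the per-protocol population. That leaves 7.4.1.3.1 as the only test of MAR for the primary endpoint, in a trial planned around 24 completers.

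**Working it through.** **Background check of the planning figure.** The point does not rest on it, but its inputs feed the illustration. SAP section 3 gives a difference of 6.7%, SD 4.5%, 16 and 8 completers, and two-sided alpha 0.05. Noncentrality = 6.7 / (4.5 × √(1/16 + 1/8)) = 6.7 / 1.949 = 3.44. With 22 degrees of freedom the power is 90.7%, against 90% stated. Also 24 / (1 − 0.20) = 30 randomized. Both figures reproduce.

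**Trace of the dataset in the printed order.**

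1. After step 1, MONODAT holds 20 datasets with monotone gaps.
2. After step 2, MONODAT holds 20 complete datasets, with treated dropouts filled from their own arm.
3. Control-based II splits MONODAT. Neither part has a gap, so both calls return the step-2 values.
4. Control-based III takes MONOREF_plus from II and inherits the same state.
5. Control-based I runs by _IMPUTATION_, and MONODAT is the only earlier dataset shown that carries this index. If membership is read from the overwritten file, no treated patient has missing data and none qualifies. If it is read from the source data, the selected patients already hold MAR values. Either way nothing is imputed from the reference group.

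**Names that do not match.** The 7.4.1.3.1 blocks call the baseline variable BASE; the two steps in 7.4.1.2 call it BASELINE. Control-based III refers to TRTGRP in its MNAR statement but lists it in neither CLASS nor VAR. These blocks may therefore stop with an error. Repairing only the names would clear the error and leave the overwrite in place.

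**Numerical illustration.** A simulation ran each control-based analysis twice, once on the overwritten data and once on preserved monotone data.

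- From the documents: 2:1 allocation (20 and 10 patients), 20 imputations, 20% loss, and a median baseline of 25.0 mm². The effect is 6.7% × 25.0 = 1.675 mm² and the SD 4.5% × 25.0 = 1.125 mm².
- Assumed: visit correlation 0.3, 0.5 or 0.8; W8 observed, with W24 and W48 missing for dropouts in both arms; a W8 effect of 1.2 mm²; half of treated dropouts classed as poor-outcome.
- Simplified: W24 analysis of covariance in place of the mixed model, no mutation term, 40 trials per setting.

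In one example trial, 6 dropouts × 2 visits = 12 missing cells before step 2, and 0 after. The MAR estimate was −1.419 (SE 0.451). As coded, I, II and III were each −1.419 (SE 0.451). With the monotone data preserved they were −1.256, −1.274 and −1.332. Over all settings, the largest difference between the as-coded results and MAR was 0.

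Mean estimates (mm²) at 20% missing with the monotone data preserved; shrinkage = 1 − estimate / MAR:

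| Correlation | MAR | I | II | III |
|---|---|---|---|---|
| 0.3 | −1.537 | −1.285 (16.4%) | −1.394 (9.3%) | −1.397 (9.1%) |
| 0.5 | −1.706 | −1.445 (15.3%) | −1.566 (8.2%) | −1.580 (7.4%) |
| 0.8 | −1.699 | −1.515 (10.8%) | −1.624 (4.4%) | −1.603 (5.7%) |

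The MAR column moves between rows because only 40 trials were run; the comparison to read is within a row. For control-based I, shrinkage was about 5-10% at 10% missing and 13-22% at 30%.

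**The case against.** The strongest reply is that this is sample code and the method in the prose is right: partition first, impute afterwards, start from the monotone data. The definition of MONOREF_all can be met only from data that still have gaps, which shows what was intended. Controls also exist. SAP 7.1.9 requires the statistician to review programs, logs and outputs, and requires double programming of the primary endpoint analysis. SAP 7.4.1 counts the sensitivity analyses as part of that analysis, so double programming can be read as covering them. SAP 12.2 adds dry runs before database lock, and results identical to MAR would be conspicuous. All of this lowers the chance that the fault survives. It does not take the fault out of the plan, and two programmers working from the same printed code can reproduce the same error.

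Some stronger readings are tempting but not supported:

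- *All three analyses will certainly show false robustness.* The parent of MONOREF_all is inferred, and the name mismatches may stop the blocks first. An analysis that stops cannot mislead; the silent result needs a partial repair.
- *The primary result is compromised.* SAP 7.4.1.1 fits observed data without imputation, and no decision rule depends on the control-based results.
- *One large attenuation applies to all three.* The larger figures belong to control-based I. Assuming that dropouts have no W8 scan would raise them, but SAP 6.1 generally keeps a patient with no follow-up scan out of the mITT population. Protocol 8.7 asks for an MRI after early discontinuation and another at V30, so 20% discontinuation need not mean 20% missing. Where W48 is present and W24 is not, step 1 fills the gap, and the control-based step would not touch it under either version of the code.

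**Conclusion.** The point holds as an inconsistency in the SAP's code that should be corrected before unblinding. In the printed order, with names repaired, control-based II and III have no missing values to fill and return the MAR result; the same follows for I if it is built from MONODAT. This conflicts with the SAP's own requirement to partition before imputing. It follows from the text and needs no simulation.

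The size of what would be hidden is less certain. It is about 11-16% (I), 4-9% (II) and 6-9% (III) of the MAR effect, given 20% missing at W24 and W48 with W8 observed, visit correlation 0.3-0.8 and half of treated dropouts classed as poor-outcome. Apart from the 20% discontinuation rate, the documents give none of these. The damage is confined to the missing-not-at-random checks of the primary endpoint.

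**What to change.** In the SAP's sample code:

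1. Write step 2 to its own dataset, for example out=DATIMP_MAR, and use that for the supportive analysis.
2. State that MONOREF_all, MONOTRT_minus and MONOREF_plus are built from the preserved step-1 monotone dataset.
3. Use one name for the baseline variable throughout (BASE or BASELINE).
4. Declare TRTGRP in the control-based III block.
5. Before each control-based imputation, confirm that the missing count matches the step-1 data. MONOREF_all should hold every gap, and MONOTRT_minus and MONOREF_plus together should hold every gap. A test for a count above zero is not enough, because one part of the split may legitimately be complete.

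The cost is a few lines of SAP text and one logged check, made before unblinding. No data collection, population or primary model changes.

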1.3 Exploratory objectives

[figure not shown]
The exploratory objectives of the study are:

- To evaluate the effect of treatment with CER-001 with respect to other efficacy measurements including carotid artery and carotid normalized wall index using 3T-MRI;
- To evaluate the effect of treatment with CER-001 with respect to potential surrogate markers on vessel wall biology including laboratory variables;
- To evaluate the effect of treatment with CER-001 with respect to inflammation;
- To evaluate plasma-mediated cellular Cholesterol efflux capacity;
- To measure ApoA-1 levels (pharmacokinetic parameters);
- To measure Cholesterols, triglycerides, lipids, apolipoprotein and lipoprotein levels (pharmacodynamics parameters).

2. Study summary

This is a phase III, multi-centre, randomized, 48 weeks, double-blind, parallel-group, placebo-controlled study to evaluate efficacy and safety of CER-001 on ApoA-1 and vessel wall area in patients with genetically defined familial primary hypoalphalipoproteinemia and receiving background optimized lipid therapy.

The study design is illustrated in the following figure:

3. Sample size

The assumptions upon which the power calculations are based are data from the 7 patients completing the CER-001-CLIN-007 SAMBA study, given the similarity of the genetic mutations. Those patients presented with a median value for MVWA of 25.0 mm² and had a follow-up median value at 6 months of 21.8 mm². The mean percent reduction is reported as 6.7%, standard deviation = 4.5%. These observed values would provide a conservative estimate of the effect of CER-001 in the more severe population for this FPHA study.

Using these results from SAMBA (i.e. an assumed standard deviation of 4.5%) and a 2:1 randomization scheme to maximize exposure to active drug, 16 completing patients in the CER-001 group and 8 in the placebo group (24 total completers for mITT) would yield 90% power to detect a difference from baseline versus placebo of 6.7%, using two-tailed testing with α =0.05. A total of 30 patients are planned to be randomized that would provide a buffer such that a 20% discontinuation rate would still allow the study to retain sufficient power for a supporting per protocol efficacy analysis (MVWA).

CER-001-CLIN-009 CER-001

4. Randomization

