7.4.1.1 Main analysis

A linear mixed model with repeated measures (MMRM) will be fitted to observed data for the mITT population without any imputation. An unstructured covariance matrix will be used to model random effects. The model will include the following variables:

- Change from baseline in carotid artery MVWA (mm², dependent variable)
- Randomized treatment group (CER-001 vs Placebo, independent variable)
- Genetic mutation (ABCA-1/ApoA-1/ABCA-1 and ApoA-1), independent variable)
- Carotid artery MVWA at W0 (mm², covariate)
- Visit (W8/W24/W48, independent variable)
- Treatment-by-Visit interaction (independent variable)
- Carotid artery MVWA at W0 by Visit interaction (independent variable)
- Treatment-by-carotid artery MVWA at W0 (independent variable)
- Subject (random factor)

Sample SAS Code

```
proc mixed data=DATASET method=reml covtest asycov alpha=0.05;

class USUBJID TRTGRP (ref="Placebo") VISIT (ref=LAST) GENETIC_MUT (ref="REF");

model CHANGE = BASELINE GENETIC_MUT BASELINE*VISIT TRTGRP VISIT

VISIT*TRTGRP BASELINE*TRTGRP / s ddfm=kr;

repeated visit / subject=USUBJID type=UN r rcorr;

lsmeans VISIT*TRTGRP / diff cl om e;

estimate "Treatment Effect" TRTGRP 1 -1 VISIT*TRTGRP 0 1 0 0 -1 0 / cl;

run;
```

Adjusted means in change from baseline for each treatment group (with 95%CI) as well as treatment effect (with 95%CI) at W24 will be provided. Treatment effect will be calculated as the difference in adjusted mean values for the two treatment groups at W24.

Adjusted means in change from baseline and treatment effect will also be estimated at W24 within each genetic mutation subgroup.

CER-001-CLIN-009 CER-001

A scatter plot will also be drawn representing the evolution of the carotid artery MVWA (mm²) according to the carotid artery MVWA at week 0 (mm²) grouped by treatment group.

Adjusted means (with 95%CI) of each randomized treatment group will also be plotted.

Results will be displayed according to table 5 of section 12.1.

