7.4.1.3.2 Analysis on the PP population

Primary efficacy analysis described for ITT population will also be performed on PP population in the same way (see sections 7.4.1.1 & 7.4.1.2).

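### SAP 7.4.1.2 pools the imputed-data results without small-sample degrees of freedom, so the supportive analysis and the imputation part of its PP repeat are slightly too lenient

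*SAP*

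**What the plan says.** The main analysis (SAP 7.4.1.1) is a repeated-measures mixed model on observed data. Its sample code asks for Kenward-Roger df: "VISIT*TRTGRP BASELINE*TRTGRP / s ddfm=kr".

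The supportive analysis (SAP 7.4.1.2) fits the same model to 20 completed data sets. The final estimate is then obtained from a printed call that begins "proc mianalyze data=MRESULTS" and reads in one estimate and one standard error per data set. The call has no EDF= option, and the SAP nowhere mentions complete-data df or a Barnard-Rubin adjustment.

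For the three control-based analyses (SAP 7.4.1.3.1) the SAP prints imputation code but no pooling code. It says only: "For each scenario, every 20 analysis estimates will be combined in one final estimate".

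The PP analysis (SAP 7.4.1.3.2) reuses both the main and the supportive method: "Primary efficacy analysis described for ITT population will also be performed on PP population in the same way".

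**The concern.** With 24 to 30 patients the reference distribution matters, and the SAP recognises this by choosing Kenward-Roger df for the main model. When PROC MIANALYZE is given only an estimate and a standard error, it takes the complete-data df as infinite. (This is general knowledge of the software and is not stated in the documents.) The small-sample correction chosen for the primary result is then dropped in the analysis meant to support it.

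The case with no missing data shows this most clearly. All 20 data sets are then identical, and the pooled estimate and standard error equal those of the main model. Yet a t of 2.05 has p = 0.055 on 18 df (0.051 on 24 df) in the main analysis and p = 0.040 as pooled. A borderline primary result could look confirmed, or even rescued, through a software default alone.

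**Working it through.** **Plan's own figure.** SAP section 3 assumes "16 completing patients in the CER-001 group and 8 in the placebo group", a difference of 6.7% and "an assumed standard deviation of 4.5"%, with two-sided alpha of 0.05 and 90% power. The standard error is 4.5 × √(1/16 + 1/8) = 1.949 and the noncentrality is 6.7/1.949 = 3.44. On 22 df (critical value 2.074) power is 90.7%, so the stated 90% is reproduced. The normal formula gives 93.0%. The planned power thus agrees with a t reference, not a normal one.

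**Inputs.**
- Number of imputations: m = 20 (SAP 7.4.1.2).
- Complete-data df: assumed 18 to 24. A week-24 covariance model with the SAP's terms has 6 parameters: intercept, treatment, baseline, treatment-by-baseline, and two for the three mutation classes. This leaves 24 − 6 = 18 or 30 − 6 = 24 df.
- Missing information λ: assumed 5 to 30%.

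**Formulas.**
- As coded (Rubin): df = (m − 1)/λ².
- With EDF= (Barnard-Rubin), for complete-data df ν: ν_obs = (ν + 1)/(ν + 3) × ν × (1 − λ), and df = 1/(1/Rubin df + 1/ν_obs).

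Example with ν = 18 and λ = 0.10: Rubin df = 19/0.01 = 1,900. ν_obs = (19/21) × 18 × 0.9 = 14.66. Barnard-Rubin df = 1/(1/1,900 + 1/14.66) = 14.5.

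| ν | λ | Rubin df | Barnard-Rubin df | Critical value as coded | Critical value with EDF= | Interval too narrow by | Size by formula |
|---|---|---|---|---|---|---|---|
| 18 | 5% | 7,600 | 15.4 | 1.960 | 2.126 | 7.8% | 6.8% |
| 18 | 10% | 1,900 | 14.5 | 1.961 | 2.137 | 8.2% | 6.9% |
| 18 | 30% | 211 | 10.8 | 1.971 | 2.206 | 10.6% | 7.5% |
| 24 | 5% | 7,600 | 21.1 | 1.960 | 2.079 | 5.7% | 6.3% |
| 24 | 10% | 1,900 | 19.8 | 1.961 | 2.087 | 6.0% | 6.4% |
| 24 | 30% | 211 | 14.5 | 1.971 | 2.138 | 7.8% | 6.8% |

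**Null simulation.** These runs used 10,000 to 15,000 trials per setting (Monte Carlo error about 0.2 points), 20:10 patients, m = 20, Bayesian regression imputation and a week-24 ANCOVA in place of the mixed model. Assumptions: visit correlation 0.3 to 0.9; scans missing completely at random; two or three mutation levels; 20% or 50% of treated dropouts classed as poor-outcome.

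| Analysis | Week-24 data missing | Size as coded | Size with EDF= |
|---|---|---|---|
| Supportive | none | 6.1% | 4.9% |
| Supportive | about 3% | 5.9–6.1% | 4.9% |
| Supportive | 10% | 5.7–5.8% | 4.4% |
| Supportive | 20% | 5.4–6.0% | 4.1–4.8% |
| Control-based I | about 3% | 4.1–4.8% | 3.3–3.8% |
| Control-based I | 10–20% | 1.2–3.9% | 0.8–3.0% |
| Control-based II | about 3% | 5.1–5.5% | 4.1–4.5% |
| Control-based II | 10–20% | 2.1–4.2% | 1.5–3.2% |
| Control-based III | 20% | 2.8–3.7% | 2.0–2.7% |

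A separate simulation of the supportive analysis (12,000 trials per setting, correlation 0.7) gave 5.9% and 6.5% at 16:8 with 1 and 2 scans missing. At 20:10 with 2 to 6 missing it gave 5.7 to 5.9%. With the correction its rates were 4.4 to 4.9%.

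**Why simulation and formula differ.** The pooled variance somewhat exceeds the true sampling variance. At 20% missing and correlation 0.6, the supportive analysis has a mean pooled variance of 0.201 against an empirical 0.189, so part of the df error is offset. In control-based I the figures are 0.316 and 0.162: imputing from a small placebo-based set inflates the pooled variance enough to outweigh the df error.

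**The case against.** **The control-based analyses.** A reader might infer that all three missing-not-at-random analyses also have intervals that are too narrow and a test above 5%. The documents do not support this. SAP 7.4.1.3.1 prints no pooling code, so the default is only inferred from 7.4.1.2. If that default is used, their intervals are 5 to 7% narrower than with EDF=, yet their size is 1.2 to 4.2% with 10 to 20% missing, which spans the planned 20% discontinuation. It slightly passes 5% only for control-based II with almost nothing missing. This part of the objection stands in full.

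**Size of the effect.** The excess is about half to one percentage point at 20:10. The 6.5% figure needs 16:8 with two further scans missing, although 16:8 is already the number left after attrition. Completed data sets contain every mITT patient with MRI data, so the df may be nearer 24 than 18. The fixed t of 2.05 is exact only when nothing is missing; otherwise imputation changes both the estimate and its standard error. All this stands and limits severity, but it does not remove the error.

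**It is sample code.** The call is labelled as a sample, and SAP 12.2 has dry-run outputs approved before database lock, so the final program could differ. But 7.4.1.2 presents this call as the way the estimates are combined, and no other text sets the df.

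**The main analysis is untouched.** True: it uses no imputation, and no stated success rule depends on a pooled p-value.

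**Conclusion.** The pooling rule in SAP 7.4.1.2 is wrong as written for a trial of this size. In the supportive analysis and the multiple-imputation part of the PP repeat, intervals are about 6 to 11% too narrow by formula and about 5 to 7% in simulation. Two-sided size is about 5.4 to 6.5% in simulation, and the excess is present even when no data are missing. The supportive analysis is therefore slightly more lenient than the result it supports.

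For the control-based analyses the only point is that the pooling df are unstated. The main model within the PP repeat keeps its Kenward-Roger df. Severity is minor to moderate: the primary conclusion cannot change, but a borderline result could seem better supported than it is.

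This rests on the MIANALYZE default, the assumed 18 to 24 df, the assumed missing information and visit correlations, and a week-24 ANCOVA standing in for the three-visit model.

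**What to change.** - In SAP 7.4.1.2, add EDF= to the PROC MIANALYZE call. Set it to the Kenward-Roger df of the week-24 treatment contrast, averaged over the 20 completed data sets, and say in one sentence that this is the Barnard-Rubin adjustment.
- In 7.4.1.3.2, apply the same rule to the multiple-imputation part of the PP analysis.
- In 7.4.1.3.1, state the same pooling method for all three scenarios, for consistency and not to correct an inflated test.

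The cost is one option and a few sentences, with no new data, and it can be settled before database lock and unblinding. Supportive intervals become slightly wider, and simulated size falls to 4.1 to 4.9%. The control-based analyses become somewhat more conservative (0.8 to 3.2% at 10 to 20% missing), which the SAP should acknowledge.
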